3.4 Pharmacokinetic (PK) Population

The PK population consists of all patients in the safety population with at least one evaluable functional dupilumab concentration result following the first dose of study drug up to Week 16. Functional dupilumab concentration will also be reported in those patients who completed the study through week 28. Patients will be analyzed according to the treatment actually received.

3.5 Anti-Drug Antibody (ADA) Population

The ADA population includes all patients in the safety population with at least one reportable ADA result (either “ADA negative” or “ADA positive”) after first dose of the IMP. Patients will be analyzed according to the treatment actually received.

4 ANALYSIS VARIABLES

4.1 Demographic and Baseline Characteristics

The following demographic and Baseline characteristics variables will be summarized:

- Demographic variables: Age at screening with grouping (year; ≥ 18 -<40, ≥ 40 -<65, ≥ 65), Sex, Race (Asian), Baseline weight with grouping (kilograms [kg], <70; ≥ 70 -<100, ≥ 100), Baseline Height (centimeters [cm]), and Baseline BMI (kg/m^2 ; <15, ≥ 15 -<25, ≥ 25 -<30, ≥ 30 ; <18.5, ≥ 18.5 -<24, ≥ 24 -<28, ≥ 28), Patients with inadequate response to topicals (Yes/No), Topical treatments are medically inadvisable for the patient (Yes/No)
- Baseline disease characteristics: Duration of AD disease with grouping (years; <26 and ≥ 26), Investigator's Global Assessment (IGA) score, Eczema Area and Severity Index (EASI) score, Pruritus numerical rating scale (NRS) for maximum or average itch intensity, Pruritus categorical scale (PCS), Body Surface Area (BSA) Involvement of Atopic Dermatitis, Patient Oriented Eczema Measure (POEM), Dermatology Life Quality Index (DLQI), and EuroQol five dimensions questionnaire (EQ-5D)

4.2 Medical History and Atopic Disease Medical History

Medical history will be coded to a Preferred Term (PT) and associated primary System Organ Class (SOC) using the version of Medical Dictionary for Regulatory Activities (MedDRA) currently in effect at Sanofi at the time of database lock.

Family history of atopic/allergic conditions will be collected, including atopic dermatitis, asthma, allergic conjunctivitis (keratoconjunctivitis), allergic rhinitis, chronic rhinosinusitis, nasal polyps, eosinophilic esophagitis, food allergy, hives and other allergies (medications, animals, plants, mold, dust mites, etc.).

4.3 Pre-treatment/ Concomitant Medications and Procedures

Medications/Procedures will be recorded from the day of informed consent until the final study visit (EOS visit). Medications will be coded to the ATC level 2 (therapeutic main group) and ATC level 4 (chemical/therapeutic subgroup), according to the latest available version of WHO Drug Dictionary (WHODD). Patients will be counted once in all ATC categories linked to the medication. Procedures will be coded to a PT and associated primary SOC using the version of MedDRA currently in effect at Sanofi at the time of database lock.

Pre-treatment medications/procedures: medications taken or procedures performed prior to administration of the first IMP. Pre-treatment medications/procedures can be discontinued before first administration or can be ongoing during treatment period.

Concomitant medications/procedures: medications taken or procedures performed following the first IMP through the EOS visit.

Background treatment: All patients are required to apply moisturizers (emollients) at least twice daily for at least the 7 consecutive days immediately before randomization and to continue throughout the study.

Prohibited concomitant medications/procedures during the study

The following treatments are prohibited during the study:

- Treatment with a live (attenuated) vaccine
- Treatment with immunomodulating biologics
- Treatment with an investigational drug (other than dupilumab)
- Treatment with TCS or TCI
- Treatment with systemic corticosteroids or nonsteroidal systemic immunosuppressive/immunomodulating drugs (eg, cyclosporine, methotrexate, mycophenolate-mofetil, azathioprine, and Janus kinase inhibitors)
- Initiation or uptitration of allergen-specific immunotherapy (SIT). Patients on SIT prior to the screening visit must be on a stable dose and remain on that dose during the study
- Any other medications for AD that could have interfered with efficacy outcomes or affected the evaluation for AD severity. Examples of such medications include coal tar products, other staining topical products, traditional Chinese medicine (TCM), or any other therapeutic agents for AD that were not properly evaluated in clinical trials

The IMP will be discontinued if the following is used through Week 16:

- Treatment with a live (attenuated) vaccine
- Treatment with immunomodulating biologics
- Treatment with an investigational drug (other than dupilumab)
- Treatment with systemic corticosteroids or nonsteroidal systemic immunosuppressive/immunomodulating drugs (eg, cyclosporine, methotrexate, mycophenolate-mofetil, azathioprine, and Janus kinase inhibitors)

The following concomitant procedures are prohibited during study participation:

- Major elective surgical procedures
- Phototherapy
- Tanning in a bed/booth

Rescue treatments for AD: If medically necessary (ie, to control intolerable AD symptoms), rescue treatment for AD with otherwise prohibited medication or procedure may be provided to study patients at the discretion of the investigator.

Patients who receive rescue treatment during the study treatment period will continue study treatment if rescue consisted of topical medications. Topical calcineurin inhibitors may be used for rescue, but should be reserved for problem areas only. If possible, Investigators should attempt to limit the first step of rescue therapy to topical medications, and escalate to systemic medications only for patients who do not respond adequately after at least 7 days of topical treatment.

If a patient receives rescue treatment with systemic corticosteroids or nonsteroidal systemic immunosuppressive/immunomodulating drugs (cyclosporine, methotrexate, mycophenolate mofetil, azathioprine, Janus kinase inhibitors, biologic agents, etc), the IMP will be immediately discontinued.

After the treatment with these medications is completed, the IMP may be resumed if deemed appropriate by the Investigator and the sponsor, but not sooner than 5 half-lives after the last dose of systemic rescue medication.

All patients will complete the schedule of study visits and assessments whether or not they complete the treatment with the IMP and whether or not they receive rescue treatment for AD. Investigators should make every attempt to conduct efficacy and safety assessments (eg, disease severity scores, safety labs) immediately before administering any rescue treatment. An unscheduled visit may be used for this purpose if necessary.

Blinded adjudication of rescue treatments will be implemented before database locks by considering the type of medication, indication, timing, frequency and the potential impact of the use of the prohibited medication or procedure. The rescue treatments will be adjudicated by the clinical study director and the adjudication procedure will be documented.

4.4 Efficacy Variables

4.4.1 Primary Efficacy Variable

The primary endpoint is:

- Proportion of patients with both IGA 0 to 1 (on a 5-point scale) and a reduction from baseline of ≥ 2 points at Week 16

Investigator's Global Assessment (IGA)

The IGA is a static 5-point assessment instrument used in clinical studies to rate the severity of AD globally. The ratings (0 = clear, 1 = almost clear, 2 = mild, 3 = moderate, 4 = severe) are an overall assessment of the skin lesions based on erythema and papulation/infiltration. The IGA score will be assessed at every scheduled and unscheduled clinic visit.

4.4.2 Secondary Efficacy Variables

The secondary endpoints are:

- Proportion of patients with EASI-75 response (reduction of EASI score $\geq 75\%$ from baseline) at Week 16
- Proportion of patients with reduction of weekly average of peak daily pruritus NRS ≥ 4 from baseline to Week 16
- Proportion of patients with reduction of weekly average of peak daily pruritus NRS ≥ 3 from baseline to Week 16
- Percent change from baseline to Week 16 in weekly average of peak daily Pruritus NRS
- Change from baseline to Week 16 in weekly average of peak daily Pruritus NRS
- Percent change in EASI score from baseline to Week 16
- Change from baseline to Week 16 in percent BSA of AD involvement
- Change from baseline to Week 16 in DLQI
- Change from baseline to Week 16 in POEM
- Percent change from baseline to Week 2 in weekly average of peak daily Pruritus NRS
- Absolute and percent change from baseline to Week 16 in EQ-5D
- Proportion of patients who achieve reduction of IGA score by ≥ 2 from baseline to Week 16
- The proportion of patients with EASI-50 ($\geq 50\%$ improvement from baseline) at Week 16
- The proportion of patients with EASI-90 ($\geq 90\%$ improvement from baseline) at Week 16

- Proportion of patients achieving IGA 0 to 1 and a reduction of ≥ 2 points from baseline through Week 16
- Absolute and percent changes in EASI score from baseline through Week 16
- Absolute and percent changes in weekly average of peak daily pruritus NRS score from baseline through Week 16
- The proportion of patients who responded “absence of pruritus” or “mild pruritus” in the pruritus categorical scale at Week 16
- Number of days and proportion of patients with sick leave/missed school days

Eczema Area and Severity Index (EASI)

The EASI is a validated measure used in clinical practice and clinical trials to assess the severity and extent of AD ([Hanifin 2001](#)). Four AD disease characteristics (erythema, thickness [induration, papulation, edema], scratching [excoriation], and lichenification) will each be assessed for severity by the Investigator or designee on a scale of “0” (absent) through “3” (severe). In addition, the area of AD involvement will be assessed as a percentage by body area of head, trunk, upper limbs, and lower limbs, and converted to a score of 0 to 6. In each body region, the area is expressed as 0, 1 (1% to 9%), 2 (10% to 29%), 3 (30% to 49%), 4 (50% to 69%), 5 (70% to 89%), or 6 (90% to 100%).

For each body region (head, trunk, upper limbs, and lower limbs), EASI score = (sum of the four AD disease characteristics scores) multiply (area of AD involvement score). The total EASI score is the weighted total of the body region EASI scores using the weights 10% = head, 20% = upper limbs, 30% = trunk, 40% = lower limbs. The minimum possible EASI score is 0 and the maximum possible EASI score is 72 where a higher score indicates increased extent and severity of AD.

The EASI will be collected at every scheduled and unscheduled clinic visit.

Pruritus Numeric Rating Scale (NRS)

The Pruritus NRS is a simple assessment tool that patients will use to report the intensity of their pruritus (itch) during a daily recall period using a pruritus reporting system. Patients will be asked the following questions:

- For average itch intensity: “On a scale of 0 to 10, with 0 being ‘no itch’ and 10 being the ‘worst itch imaginable’, how would you rate your itch overall (on average) during the previous 24 hours?”
- For maximum itch intensity: “On a scale of 0 to 10, with 0 being ‘no itch’ and 10 being the ‘worst itch imaginable’, how would you rate your itch at the worst moment during the previous 24 hours?”

Patients will be instructed on using the pruritus reporting system to record their Pruritus NRS score at the screening visit. Patients will complete the rating scale daily. Clinical sites will receive alerts when patients do not complete the pruritus reporting system items. Sites will be expected to contact patients who have missed 2 consecutive entries to encourage patient compliance. The Investigator will check patients’ reports at each visit.

If there are multiple NRS to the same question (average or maximum itch intensity) collected on the same day, average of all the scores collected will be taken.

The baseline NRS is defined as the prorated average of the NRSs reported continuously for 7 days right before and on the baseline visit (i.e. study day -6 to day 1). For post-baseline NRS, The mean weekly NRS is calculated as the prorated average of the reported daily NRS within the week. For example, if there are 3 scores in a week, the prorated average = (score1 + score2 + score3)/3. The baseline NRS and mean weekly NRS will be calculated for average itch intensity and peak itch intensity separately.

Body Surface Area (BSA) Involvement of Atopic Dermatitis

Body surface area affected by AD will be assessed for each section of the body (the possible highest score for each region is: head and neck [9%], anterior trunk [18%], back [18%], upper limbs [18%], lower limbs [36%], and genitals [1%]) and will be reported as a percentage of all major body sections combined. Patients will undergo this assessment at every scheduled and unscheduled clinic visit.

Dermatology Life Quality Index (DLQI)

The DLQI is a 10-item, validated questionnaire ([Badia 1999](#)) used in clinical practice and clinical trials to assess the impact of AD disease symptoms and treatment on Quality of Life (QOL). The format is a simple response to (0 to 3, where 0 = not at all; 1 = a little, 2 = a lot, 3 = very much) 10 questions, which assess QOL over the past week, with an overall scoring system of 0 to 30; a high score is indicative of a poor QOL. For question 7, 0 = not relevant, 1 = no + a little, 2 = no + a lot, 3 = yes. For general inflammatory skin conditions a change in DLQI score of at least 4 points is considered clinically important ([Basra et al, 2015](#)). The DLQI will be assessed at every scheduled and unscheduled clinic visit.

Handling missing items from DLQI:

- i. If one question is left unanswered this is scored 0 and the scores are summed and expressed as usual out of a maximum of 30.
- ii. If two or more questions are left unanswered the questionnaire is not scored.
- iii. If question 7 is answered 'yes' this is scored 3 even if in the same question one of the other boxes is ticked.
- iv. If question 7 is answered "no" or "not relevant", but either 'a lot' or 'a little' is ticked this is then scored 2 or 1.
- v. If two or more response options are ticked for one question, the response option with the highest score should be recorded.

Patient Oriented Eczema Measure (POEM)

The POEM is a 7-item, validated questionnaire used in clinical practice and clinical trials to assess disease symptoms in children and adults ([Charman 2004](#)). The format is a response to 7 items (dryness, itching, flaking, cracking, sleep loss, bleeding, and weeping) based on frequency during the past week (ie, 0 = no days, 1 = 1 to 2 days, 2 = 3 to 4 days, 3 = 5 to 6 days, and 4 = all days) with a scoring system of 0 to 28; the total score reflects disease-related morbidity.

If two or more response options are selected for a question, then the response option with the highest score is recorded. If one question of the seven is left unanswered, then that question is scored as 0 and the scores are summed and expressed as usual out of a maximum of 28. If two or more questions are left unanswered, then the questionnaire is not scored and is set to missing.

The POEM will be assessed at every scheduled and unscheduled clinic visit.

EuroQol five dimensions questionnaire (EQ-5D)

The EuroQoL 5-Dimension Health Questionnaire 3 Level (EQ-5D-3L) is a standardized measure of health status developed by the EuroQOL Group in order to provide a simple, generic measure of health for clinical and economic appraisal. The EQ-5D-3L is a self-administered questionnaire used to assess health status ‘today’ which consists of 2 parts: the descriptive system and the EQ visual analogue scale (EQVAS).

The descriptive system comprises the following 5 dimensions: mobility, self-care, usual activities, pain/discomfort, and anxiety/depression. Each dimension has 3 levels of perceived problems: “no problem” (level 1), “some problems” (level 2), “extreme problems” (level 3). The respondent is asked to indicate his/her health state by ticking (or placing a cross) in the box against the most appropriate statement (ie, no problems, some problems, or severe problems) in each of the 5 dimensions; this results in a 1-digit number expressing the level for that dimension. The digits for 5 dimensions can be combined in a 5-digit number describing the respondent’s health state, potentially producing 243 different states. Health states defined by the 5-dimensional classification can be converted into corresponding index scores that quantify health status, where 0 represents “death” and 1 represents “perfect health.” Values for the 243 theoretically possible health states defined by the EuroQol classification are calculated using a regression model and weighted according to the social preferences of the Chinese population. The minimum value for the single index utility score is 0.1702. [Appendix 10.4](#) provides the SAS code to derive the index utility score using Chinese based population ([Zhu, 2018](#)).

The EQVAS records the respondent’s self-rated health on a vertical, visual analogue scale where the endpoints are labeled “best imaginable health state (100)” and “worst imaginable health state (0)”. This information can be used as a quantitative measure of health outcome as judged by the individual respondents.

EQ-5D-3L will be assessed at the following visits: baseline (Day 1), Week 8, Week 16 (EOT), Week 28 (EOS), and early termination (ET) visit.

Pruritus Categorical Scale (PCS)

The PCS is a 4-point scale used to assess symptoms that has been used in clinical studies of AD and there is less of a tendency for patients to provide an “average” response than there might be with a 5-point scale ([Kaufmann 2006](#)). The scale is rated as follows: 0: absence of pruritus; 1: mild pruritus (occasional slight itching/scratching); 2: moderate pruritus (constant or intermittent itching/scratching that does not disturb sleep) and 3: severe pruritus (bothersome itching/scratching that disturbs sleep).

Patients will be instructed on using the pruritus reporting system to complete the PCS at the screening visit. Patients will complete the categorical scale daily. Clinical sites will receive alerts when patients do not complete the pruritus reporting system items. Sites will be expected to contact patients who have missed 2 consecutive entries to encourage patient compliance. The Investigator will check patients’ reports at each visit.

For each day, if there are multiple PCS scores collected on the same day, the maximum (worst) of all the scores collected will be chosen. For each week, calculate round prorated average of

collected scores for Category Score. For example, if there are 3 scores in a week, the prorated average = (score1 + score2 + score3)/3 round to 1.0.

The baseline PCS is defined as the round prorated average of the PCSs reported continuously for 7 days right before and on the baseline visit (i.e. study day -6 to day 1).

Sick Leave/Missed School Days

Patients who are employed or enrolled in school will be asked to report the number of sick leave/missed school days since the last study assessment. Patients will undergo this assessment at the following visits: baseline (Day 1), Week 4, Week 8, Week 12, Week 16 (EOT), Week 20, Week 24, Week 28 (EOS), ET and unscheduled visits.

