7.1 INCLUSION CRITERIA

A patient must meet the following criteria to be eligible for inclusion in the study:

- I 01. Male or female, 18 years or older
- I 02. Atopic dermatitis (according to American Academy of Dermatology Consensus Criteria, 2014) (1) that has been present for at least 3 years before the screening visit
- I 03. EASI score ≥ 16 at the screening and baseline visits
- I 04. IGA score ≥ 3 (on the 0 to 4 IGA scale, in which 3 is moderate and 4 is severe) at the screening and baseline visits
- I 05. $\geq 10\%$ BSA of AD involvement at the screening and baseline visits
- I 06. Baseline Pruritus NRS average score for maximum itch intensity ≥ 4

NOTE: Baseline Pruritus NRS average score for maximum itch intensity will be determined based on the average of daily NRS scores for maximum itch intensity (the daily score ranges from 0 to 10) during the 7 days immediately preceding randomization. A minimum of 4 daily scores out of the 7 days is required to calculate the baseline average score. For patients who do not have at least 4 daily scores reported during the 7 days immediately preceding the planned randomization date, randomization should be postponed until this requirement is met, but without exceeding the 35-day maximum duration for screening

- I 07. Documented recent history (within 6 months before the screening visit) of inadequate response to treatment with topical medications or for whom topical treatments are otherwise medically inadvisable (eg, because of important side effects or safety risks);

NOTE:

- Inadequate response is defined as failure to achieve and maintain remission or a low disease activity state (comparable to IGA 0 = clear to 2 = mild) despite treatment with a daily regimen of TCS of medium to higher potency (\pm TCI as appropriate), applied for at least 28 days or for the maximum duration recommended by the product prescribing information (eg, 14 days for super-potent TCS), whichever is shorter.
- Patients with documented systemic treatment for AD, of sufficient dose and duration, in the past 6 months are also considered as inadequate responders to topical treatments

and are potentially eligible for treatment with dupilumab after appropriate washout, subject to approval by the sponsor.

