5.7.2 Analyses of Secondary Efficacy Variables

The binary secondary efficacy endpoints will be analyzed using the same approach as that used for the analysis of the primary endpoints.

The continuous endpoints will be analyzed using the multiple imputation (MI) with analysis of covariance (ANCOVA) model as the primary analysis. Patients' efficacy data after rescue medication or procedure up to Week 16 or after study withdrawal up to Week 16 will be set to missing and then imputed by the MI method. Missing data from the ITT population will be imputed 50 times to generate 50 complete data sets by using the SAS MI procedure (using Markov Chain Monte Carlo method) following the 2 steps below:

Step 1: The monotone missing pattern is induced by Markov Chain Monte Carlo (MCMC) method in MI procedure. The monotone missing pattern means that if a patient has missing value for a variable at a visit, then the values at all subsequent visits for the same variable are all missing for the patient.

Step 2: The missing data at subsequent visits will be imputed using the regression method for the monotone pattern with adjustment for covariates including treatment group, randomization strata (disease severity), and relevant baseline value.

The Week 16 data of each of the 50 complete datasets will be analyzed using an ANCOVA model with treatment, randomization strata (disease severity), and relevant baseline value included in the model, and the SAS MIANALYZE procedure will be used to generate valid statistical inferences by combining results from the 50 analyses using Rubin's formula.

The imputation model will include:

- The variables in the ANCOVA model, including treatment group, randomization strata and relevant baseline value
- Measured continuous endpoint values in each scheduled visit up to Week 16

Categorical variables included in above model (ie, treatment group and randomization strata) are not expected to be missing.

To account for the impact of rescue medication or procedure or dropouts on the efficacy effect:

- If a patient receives rescue medication or procedure that specifies the patient as a non-responder according to the above rules for binary efficacy endpoints, the data collected after rescue medication or procedure is initiated will be treated as missing.
- If a patient withdraws from the study, the data collected after study withdrawal will be treated as missing

Sensitivity analyses

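### The categorical itch endpoint (absent or mild at Week 16) is tested without its own baseline; adding baseline PCS as a CMH stratum would recover some precision at little cost

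*SAP*

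**What the plan says.** **Endpoint.** Protocol 9.2.1 and SAP 4.4.2 list, as a secondary endpoint, the proportion reporting absent or mild itch "in the pruritus categorical scale at Week 16". No change from baseline is asked for. The other IGA, EASI and itch responder endpoints in the same list all require one: IGA 0-1 with a fall of at least 2, IGA fall of at least 2, EASI-50, EASI-75 and EASI-90, and NRS falls of at least 3 and at least 4.

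**Score.** PCS is a daily 4-point scale (0 to 3). For each week the SAP says to "calculate round prorated average of" the collected scores, so a weekly mean from 0.5 to just under 1.5 becomes 1 (mild). The baseline is built the same way: "The baseline PCS is defined as the round prorated average of the PCSs reported continuously for 7 days" (SAP 4.4.2, study days -6 to 1).

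**Test.** SAP 5.7.2 states: "The binary secondary efficacy endpoints will be analyzed using the same approach as that used for the analysis of the primary endpoints". Under SAP 5.7.1 that is a CMH test stratified by baseline disease severity (IGA 3 or 4). Patients with rescue, withdrawal or a missing Week 16 value count as non-responders. Continuous endpoints, by contrast, are adjusted for their own baseline value by ANCOVA (SAP 5.7.2).

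**Entry.** Itch eligibility (Protocol 7.1, I 06) rests on the "Baseline Pruritus NRS average score for maximum itch intensity", which must be at least 4. There is no PCS criterion.

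**Status.** The PCS endpoint is not among the 12 secondary endpoints in the hierarchy of SAP 5.7.2, and no power is stated for it.

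**The concern.** PCS is the one symptom responder endpoint whose own baseline appears neither in its definition nor in its test. A patient can meet the entry rule on worst-moment itch and still have a rounded weekly PCS of 1. If that patient is unchanged at Week 16, the result is a success in whichever arm the patient was assigned to. Where such patients succeed equally often in both arms, they raise both proportions and shrink the difference between them. A strong predictor of outcome is then left out of the test although it is available. What is at stake is precision on one endpoint outside the hierarchy, and how readily its proportion can be read as improvement.

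**Working it through.** **1. The plan's own figure.** SAP 2.2 states 94% power for the primary IGA endpoint: 80 per arm, 37% versus 12%, two-sided 0.05, continuity-corrected chi-square. The correction gives an effective size of (80 - 1/0.25)²/80 = 76²/80 = 72.2 per arm. Then:
- null SE = √(2 × 0.245 × 0.755/72.2) = 0.0716
- alternative SE = √((0.37 × 0.63 + 0.12 × 0.88)/72.2) = 0.0685
- z = (0.25 - 1.96 × 0.0716)/0.0685 = 1.60, power 94.5%.

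The stated 94% reproduces. It does not cover the PCS endpoint.

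**2. Inputs for the PCS endpoint.** From the documents: 80 per arm and two-sided 0.05. Assumed, because the documents give none of them:
- share f at baseline PCS 0-1, from 2% to 20%
- Week 16 response of 45% versus 25% in patients at baseline PCS 2-3
- 85% of patients at baseline PCS 0-1 still there at Week 16, in both arms.

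The IGA stratum and the continuity correction are left out of both tests compared below.

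**3. Planned test.** Arm rates are p₁ = (1-f) × 0.45 + f × 0.85 and p₂ = (1-f) × 0.25 + f × 0.85. With p̄ their mean, z = (p₁ - p₂)/√(2p̄(1-p̄)/80), and power is Φ(z - 1.96).

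At f = 10%: p₁ = 0.405 + 0.085 = 0.49, p₂ = 0.225 + 0.085 = 0.31, p̄ = 0.40. So z = 0.18/√0.006 = 0.18/0.0775 = 2.32, power 64%.

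**4. Test stratified by baseline PCS.** Each stratum has weight n/2, where n is its size per arm. The pooled rate is 0.35 in PCS 2-3 and 0.85 in PCS 0-1.

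At f = 10%: the numerator is 36 × 0.20 + 4 × 0 = 7.2. The variance is 36 × 0.35 × 0.65 + 4 × 0.85 × 0.15 = 8.19 + 0.51 = 8.70. So z = 7.2/√8.70 = 2.44, power about 68%.

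| Share at PCS 0-1 | Difference (points) | z planned | z stratified | Power planned | Power stratified | Gain (points) |
|---|---|---|---|---|---|---|
| 2% | 19.6 | 2.58 | 2.61 | 73.3% | 74.2% | about 1 |
| 5% | 19.0 | 2.48 | 2.55 | 69.9% | 72.2% | about 2 |
| 10% | 18.0 | 2.32 | 2.44 | 64.2% | 68.5% | about 4 |
| 20% | 16.0 | 2.03 | 2.22 | 53.0% | 60.3% | about 7 |

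**5. Dependence on equal retention.** At f = 10%, lower only the placebo retention:
- 85% versus 70%: planned 71.4%, stratified 74.4%, restricted to baseline PCS 2-3 71.1%
- 85% versus 65%: planned 73.7%, stratified 76.3%, restricted 71.1%.

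Stratifying still gains about 3 points. Restriction gives slightly less power than the planned test.

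**6. Other response rates.** With 37% versus 12% in the other patients, simulation (40,000 runs) gives two contrasting cases.
- Every patient at PCS 0-1 succeeds in both arms: planned 92.5%, 87.2% and 73.3% at f = 5%, 10% and 20%; stratified 95.9%, 95.1% and 92.1%.
- 90% versus 50% of them succeed: planned 96.7%, 96.6% and 97.1%, so dilution costs nothing; stratified 97.3%, 97.9% and 98.8%.

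**7. Validity.** Simulated type I error was 4.7% to 5.1% across the null runs, with and without the PCS stratum.

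**The case against.** The strongest reply is that nothing here needs repair. Entry requires mean peak NRS of at least 4, EASI of at least 16, IGA of at least 3 and BSA of at least 10% after washout of active treatment. Mild on the PCS means only occasional slight itching, and when a day has several PCS scores the worst is kept. Few patients may enter at 0-1. The endpoint carries no confirmatory claim. A state measure is a legitimate complement to the four Week 16 NRS change endpoints, all of which are in the hierarchy. Baseline PCS is also already due to be tabulated by arm (SAP 4.1, 5 and 5.1). All of this stands, and it limits the point to an improvement.

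It also rules out stronger readings that a reader might draw:
- *That the comparison is biased or its error rate inflated.* Randomisation protects the comparison, and simulated type I error is nominal.
- *That the endpoint is unadjusted.* The test is stratified by baseline IGA severity; only baseline PCS is left out.
- *That power is certainly lost.* The loss needs a non-trivial share at PCS 0-1 and similar retention in both arms. The documents establish neither.
- *That patients already at PCS 0-1 carry no information.* They can worsen, be rescued or go missing, and then count as non-responders.
- *That the test should be restricted to baseline PCS 2-3.* Restriction drops randomised patients and can lose power (step 5).

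What the reply does not answer is why a baseline that is already derived should stay out of the test, when continuous endpoints use theirs.

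**Conclusion.** The point holds as a low-cost improvement. The definition contains no baseline PCS, and the test omits it. The likely gain from including it is small: about 1 to 4 points of power for shares of 2% to 10%, and about 7 at 20%. These figures rest on the assumed 45% versus 25% response and equal 85% retention. They also ignore the IGA stratum; if IGA severity and baseline PCS are correlated, the planned test already captures part of the gain. If almost nobody enters at PCS 0-1, the stratified test is practically the planned one. The primary analysis and the hierarchy do not change in any case.

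**What to change.** In SAP 5.7.2, state that for the PCS endpoint the CMH test is stratified by baseline PCS (0-1 versus 2-3) as well as baseline IGA severity, in the ITT population, with the endpoint definition and non-responder rules unchanged. Add one line saying which stratum takes a patient with no baseline PCS.

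The proportion among patients with baseline PCS of at least 2 may be shown as a descriptive supportive summary, not as a replacement test. No new table of baseline PCS is needed.

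The cost is a sentence or two of SAP text and one extra stratification variable from data already collected. With a very small share, a PCS 0-1 stratum may hold patients from one arm only. Such a stratum adds nothing to the CMH statistic, and the few patients in it drop out of the test. SAP section 1 allows revision on blinded review before final database lock. The change should also precede the first-step analysis that SAP section 7 permits once all patients complete the 16-week treatment period.
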